### **6.1.2 Descriptive analyses**

The raw total Mayo scores and subscores will be listed by treatment group, subject and visit/time. Descriptive statistics of both the raw and change from baseline at 2-week and 8-week visit will be provided by treatment group when relevant.

#### **6.1.2.1 Graphical presentation of results**

Scatter plots to visualize trends over time in total Mayo score, CCI and individual endoscopic, stool frequency, rectal bleeding and PhGA subscores will be created by treatment group.

### **6.1.3 Statistical model, assumptions and hypotheses**

The binary endpoint of clinical remission rate (Yes/No) will be modelled with binomial distribution and analyzed via Bayesian approach with baseline total Mayo score and treatment group as explanatory variables, to compare the remission rates between the LYS006 and placebo groups.

Prior distributions:

- LYS006 group: Clinical remission rate\_LYS006 ~ Beta (1/3, 1/3)
- Placebo group: Clinical remission rate\_Placebo ~ Beta (18.9, 167.4), Beta (3.2, 24.2), Beta (1.0, 3.3) and Beta (1,1)

The clinical remission rate for the LYS006 group will be given a neutral prior (Kerman 2011), Beta (1/3, 1/3). The clinical remission rate for the placebo group will be given an informative prior derived via the meta-analytic predictive (MAP) approach (Neuenschwander et al. 2010 and Schmidli et al. 2014). This prior is based on the control groups from a number of historical UC trials (Rutgeerts et al. 2005, Reinisch et al. 2011, Sandborn et al. 2012 and Ito et al. 2010) and the selection of historical UC studies was based on patient population and the endpoint. The MAP prior for the placebo remission rate will be a mixture of the following four beta-distributions, Beta (18.9, 167.4), Beta (3.2, 24.2), Beta (1.0, 3.3) and Beta (1, 1), with the mixture weights being 0.43, 0.34, 0.03 and 0.2 respectively. The last non-informative component is added to robustify the outcome in case of any difference between within-study placebo group and those from the historical studies.

With the specified priors and the observed remission rates from this study, the posterior distributions for clinical remission rates in LYS006 and placebo groups will be computed. The posterior probabilities as defined in the dual efficacy criteria below will be provided, along with the posterior remission rates by group and the treatment difference with 90% credible intervals.

The dual efficacy criteria are defined as ("diff" refers to the difference of true remission rates in LYS006 and placebo):

- (1) EoT clinical remission rate better than placebo with high confidence (90%), i.e.,  $\text{Prob}(\text{diff} > 0) > 90\%$ , and
- (2) Average magnitude of effect on EoT clinical remission rate  $> 15\%$  over placebo, i.e.,  $\text{Prob}(\text{diff} > 15\%) > 50\%$ .

### 6.1.3.1 Model checking procedures

Subjects who discontinued from the study for reasons other than COVID-19 before the EoT visit, or have received rescue or prohibited medication for the treatment of UC during the treatment period will be considered failed to achieve clinical remission. Any CCI data for a subject that were recorded at or after the start of a rescue or prohibited medication should be removed from the CCI statistical analyses.

Any missing subscore will lead to a non-evaluable clinical remission status and the subject will also be considered failed to achieve clinical remission. Reasons for missing Mayo scores or subscores need to be collected to understand the impact of such analysis approach. Imputation methods such as tipping point analysis may be explored.

Discontinuation prior to EoT, or subjects for which central reading of EoT endoscopy was not available due to local COVID-19 related restrictions will be considered as missing data.

Commercially Confidential Information

The homogeneity of the total Mayo scores between subjects  
visually by each visit.

CCI  
will be explored

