	 Any systemic immunosuppressant or immunomodulator, such as cyclosporine, methotrexate, azathioprine within 6 weeks and cyclophosphamide within 3 months, prior to screening endoscopy
	 A dose of > 10 mg/d prednisone or equivalent in the last 4 weeks prior to screening endoscopy. Oral budesonide is allowed if the dose is ≤ 9 mg/day with a stable dose administered for at least 4 weeks prior to the screening endoscopy.
Study treatment	LYS006 20 mg BID: 8 weeks
oracy arounders	Matching placebo BID: 8 weeks
Key Efficacy	Mayo Score based on:
assessments	Stool frequency
	Rectal bleeding
	Endoscopic findings
	Physician's Global Assessment
Other assessments	Commercially Confidential Information
Key safety	AE, SAE monitoring
assessments	Physical examinations
	Monitoring of laboratory safety
	• ECGs
	Vital signs
Data analysis	The primary endpoint of this study is the clinical remission rate at End of treatment (EoT) CCI and Week 8 for subsequent protocol amendments), i.e. the proportion of patients reaching the status of clinical remission. This primary endpoint of clinical remission is based on full Mayo score, defined as a Mayo score ≤2 with no individual subscore >1. Patients who discontinue for reasons other than COVID-19, or receive any rescue medication before EoT will be considered as treatment failure. This binary endpoint will be analyzed with a Bayesian approach, to compare the remission rates between LYS006 and placebo group. An informative prior will be used for the remission rate for placebo (refer to Sample Size section for details) and a neutral prior (Kerman 2011), Beta (1/3, 1/3), for LYS006. The posterior probabilities as defined in the dual efficacy criteria detailed in the

	analysis of the primary endpoint section will be provided, along with the posterior remission rates by group and the treatment difference with 90% credible intervals.
Key words	Ulcerative colitis, efficacy, safety

Protocol No. CLYS006X2202

1 Introduction

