12.4.1 Definition of primary endpoint: Clinical remission

The primary endpoint of this study is the clinical remission rate at the End of treatment (EoT) visit (CCI Week 8 for subsequent protocol amendments), i.e. the proportion of the patients who reach the status of clinical remission at the EoT visit.

Clinical remission is defined as a full Mayo score of 2 points or lower, with no individual subscore exceeding one point.

Subjects with early discontinuation for reasons other than COVID-19 before the EoT visit, or use of rescue/prohibited medication during the treatment period, or missing endoscopy score at EoT will be considered failed to reach remission.

Discontinuation prior to the defined treatment period, or subjects who were not able to complete endoscopy at EoT visit due to local COVID-19 related restrictions will be considered as missing data.

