### 1.3 Study objectives

#### 1.3.1 Primary Objective

Primary objective	Endpoint related to primary objective

To assess the induction of clinical remission by LYS006 in patients with mild to moderate ulcerative colitis (UC) compared to placebo

	

Clinical remission rate at Week 8 using the full Mayo score

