#### **6.1.1 Variables**

The primary PD variable of this study is the clinical remission rate at the EoT visit CCI, i.e. the proportion of patients who reach the status of clinical remission at the EoT visit.

Clinical remission is based on total Mayo score, defined as a total Mayo score of 2 points or lower, with no individual subscore exceeding one point. The total Mayo score is the sum of four subscores, ranging from 0 to 12: stool frequency (recorded on a daily basis by a diary card), rectal bleeding (recorded on a daily basis by a diary card), endoscopic findings and Physician's

Global Assessment (PhGA). Each subscore grading ranges from 0 to 3, from free of disease to severe disease.

The stool frequency subscore should be calculated from the most recent three consecutive days within the week prior to the day of endoscopy bowel preparation. If three consecutive days are not available, the most recent non-consecutive 3 days within the week prior to the day of endoscopy bowel preparation should be used. The stool frequency subscore is the average of the 3 daily stool frequency subscores. The rectal bleeding subscore will be calculated in the same manner as stool frequency subscore.

Commercially Confidential Information

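### SAP 6.1.3.1 classes a COVID-19-missing EoT endoscopy as both a failure and missing data; the protocol has the same clash, and both need one ordered rule

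*SAP*

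**What the plan says.** SAP 6.1.3.1 has three statements on who counts as a non-remitter.

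- Discontinuation: "Subjects who discontinued from the study for reasons other than COVID-19 before the EoT visit" are failures, as are users of rescue or prohibited UC medication.
- Missing subscore: "Any missing subscore will lead to a non-evaluable clinical remission status and the subject will also be considered failed to achieve clinical remission".
- COVID-19: the status of missing data goes to "Discontinuation prior to EoT, or subjects for which central reading of EoT endoscopy was not available due to local COVID-19 related restrictions".

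Protocol 12.4.1 lists, among the failures, "missing endoscopy score at EoT will be considered failed to reach remission". Its next sentence says that "subjects who were not able to complete endoscopy at EoT visit due to local COVID-19 related restrictions will be considered as missing data". Protocol 12.4.3 repeats the COVID-19 sentence beside a rule that fails any missing Week 8 subscore. In both protocol sections the COVID-19 sentence opens with discontinuation before the defined treatment period, where the SAP has discontinuation before EoT.

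On visit timing, SAP 1.3.1 gives the endpoint as "Clinical remission rate at Week 8 using the full Mayo score", and SAP 6.1.1 gives "the proportion of patients who reach the status of clinical remission at the EoT visit". The protocol summary says: "Patients who discontinue for reasons other than COVID-19, or receive any rescue medication before EoT will be considered as treatment failure".

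**The concern.** A binary primary endpoint needs each subject to have exactly one status. Here the text gives two.

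1. **COVID-19 endoscopy.** The missing-subscore sentence makes the subject a failure. The COVID-19 sentence makes the same subject missing. A subject who discontinues because of COVID-19 and has no EoT subscores meets the same overlap.
2. **Discontinuation.** If the COVID-19 qualifier in the last SAP sentence attaches only to the endoscopy limb, all early discontinuation becomes missing data. The first sentence of the section makes non-COVID-19 discontinuation a failure.

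Failed keeps the subject in the denominator; missing presumably takes the subject out. With 30 and 15 subjects that can decide whether both efficacy criteria are met, and an unresolved text lets the choice be made after the data are seen.

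**Working it through.** **The passages side by side**

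| Subject | Reading 1 | Reading 2 |
|---|---|---|
| EoT endoscopy unavailable, COVID-19 restrictions | Failed (SAP missing-subscore sentence; protocol 12.4.1 missing-endoscopy clause; protocol 12.4.3 missing-subscore sentence) | Missing (COVID-19 sentence in all three sections) |
| COVID-19 discontinuation, no EoT subscores | Failed (SAP missing-subscore sentence) | Missing (SAP COVID-19 sentence) |
| Non-COVID-19 discontinuation before EoT | Failed (SAP first sentence) | Missing (SAP last sentence, read literally) |

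No visible sentence ranks these rules or says how missing data enter the binomial counts.

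**Inputs.** 30 versus 15 subjects and a 25-point difference (protocol 12.8). Priors (protocol 12.4.2, SAP 6.1.3): LYS006 Beta(1/3, 1/3); placebo a mixture of Beta(18.9, 167.4), Beta(3.2, 24.2), Beta(1.0, 3.3) and Beta(1, 1) with weights 0.43, 0.34, 0.03 and 0.2. Both criteria must hold: P(diff>0) > 0.90 and P(diff>0.15) > 0.50.

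**Assumptions.** Missing means left out of numerator and denominator. The baseline Mayo covariate in SAP 6.1.3 is ignored. The placebo rate is not in the visible text; 11.7% is used (so 36.7% on LYS006). The frequency of affected subjects is not given; 3% and 5% per arm are used.

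**Formulas.** With y remitters of n in each arm (T = LYS006, C = placebo):
- LYS006 posterior: Beta(1/3 + y_T, 1/3 + n_T − y_T).
- Placebo posterior: mixture of Beta(a_k + y_C, b_k + n_C − y_C), with weights proportional to w_k × B(a_k + y_C, b_k + n_C − y_C) / B(a_k, b_k).
- P(diff>d) = ∫ f_C(p) [1 − F_T(p + d)] dp, by numerical quadrature.
- P(dual) = sum of binomial probabilities over all outcomes that meet both criteria.

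**Reproducing the plan's figure.** P(dual) at 36.7% versus 11.7% is 86.4%; the protocol states 86%. It is 85.0% at a placebo rate of 10%, 86.6% at 12% and 87.4% at 15%. With no difference, at 12% in both arms, it is 2.3% (stated: below 5%). The design figures are not in dispute.

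**Average effect of the two readings (COVID-19 subjects only)**

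| Affected | P(dual), failed | P(dual), left out | Difference | Decisions that change |
|---|---|---|---|---|
| 3% | 84.6% | 85.5% | 0.9 points | 1.6% |
| 5% | 83.2% | 85.0% | 1.8 points | 2.7% |
| 5%, no true difference | 1.7% | 2.0% | 0.3 points | – |

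The gap grows with frequency. With exactly 4 LYS006 and 2 placebo subjects affected (6/45 = 13.3%) and placebo rates of 10 to 12%, P(dual) is 73.8–77.2% if they are failures and 82.5–84.9% if they are left out.

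**Borderline data sets**

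| LYS006 | Placebo | LYS006 posterior | P(diff>0) | P(diff>0.15) | Dual criteria |
|---|---|---|---|---|---|
| 10/30 | 4/15 | Beta(10.33, 20.33) | 0.892 | 0.558 | Not met |
| 10/29 | 4/15 | Beta(10.33, 19.33) | 0.902 | 0.593 | Met |
| 7/30 | 1/15 | Beta(7.33, 23.33) | 0.961 | 0.432 | Not met |
| 7/29 | 1/15 | Beta(7.33, 22.33) | 0.966 | 0.470 | Not met |
| 7/28 | 1/15 | Beta(7.33, 21.33) | 0.970 | 0.509 | Met |

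In the first pair one LYS006 subject moves from failed to left out and the first criterion flips. In the second set two subjects must move before the second criterion flips.

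**Secondary point: brought-forward EoT visit.** Protocol 9.1.1 keeps a subject who stops treatment in the study and asks for the EoT visit soon after the last dose. SAP 6.1.3.1 and protocol 12.4.3 fail those who discontinue from the study; the protocol summary and 12.4.1 refer to discontinuation more broadly. If an early EoT visit yields a full Mayo score, the narrower wording does not by itself fail a non-rescued early stopper. One such remitter would move 7/30 versus 2/15 (P(diff>0.15) 0.369, not met) to 8/30 versus 2/15 (0.518, met).

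**The case against.** The natural reading is that the specific COVID-19 sentence overrides the general one and that its qualifier covers both limbs. The first SAP sentence, which sets COVID-19 discontinuation apart, supports this. It is probably the intent, and the fix adopts it. But nothing visible states it, and redacted text next to SAP 6.1.3.1 and in protocol 12.4.3 cannot be assumed either to settle or to leave open the precedence.

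It is also fair that the average effect is small, that the frequencies are assumed, and that the borderline data sets are selected: at the assumed rates 10/30 versus 4/15 has probability 0.9% and 7/30 versus 1/15 has 1.5%. The trial is a non-confirmatory proof of concept. This limits the size of the problem. It does not remove the double status.

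Two stronger readings are tempting and not supported.

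- A reader might infer that the SAP departs from the protocol on discontinuation. Protocol 12.4.3 has essentially the SAP's wording, tied to leaving the study before the EoT visit; only the summary and 12.4.1 are broader. The clash on endoscopy also comes from the protocol.
- A reader might infer that the SAP would count a brought-forward EoT score as Week 8 remission. SAP 6.1.1 has a redaction directly after the EoT visit, at the point where protocol 12.4.1 mentions Week 8. The assessment schedule, which would show whether an early EoT visit includes endoscopy, is not in the text. If it does not, the missing-subscore rule already makes the subject a failure. Rescued subjects fail in any case.

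**Conclusion.** The concern holds on the classification rules: the visible text of SAP 6.1.3.1, protocol 12.4.1 and protocol 12.4.3 gives a COVID-19-missing EoT endoscopy two statuses on the primary endpoint, and the SAP's last sentence, read literally, contradicts its first. On the assumptions listed, the choice shifts P(dual) by about 1 to 2 points and changes up to 2.7% of decisions at 5% affected; more if COVID-19 losses were heavier. One or two subjects can reverse a borderline result, which is the reason to settle the rule before unblinding. The brought-forward EoT question is only a conditional alignment point, because redacted text or the assessment schedule may already answer it.

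**What to change.** Use one ordered rule in SAP 6.1.3.1 and in protocol 12.4.1 and 12.4.3:

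1. Non-COVID-19 discontinuation before the EoT/Week 8 visit, or rescue or prohibited UC medication during treatment, is non-remission.
2. Any missing subscore is non-remission.
3. The only exception to step 2 is COVID-19 discontinuation, or an EoT endoscopy unavailable because of COVID-19 restrictions. These subjects are missing data and are left out of the binomial counts.

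Add one sensitivity analysis that counts the subjects in step 3 as failures. Replace the differing discontinuation phrases in the COVID-19 sentences of the two documents with step 3.

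Unless redacted text or the assessment schedule already settles it, also align the discontinuation wording across the protocol summary, 12.4.1, 12.4.3 and the SAP, so that an early treatment stopper's brought-forward EoT score is not counted as Week 8 remission. If a precedence or timing rule already exists in redacted text, refer to it.

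The cost is wording in two documents and one extra table. Reasons for missing Mayo scores are already to be collected, and the SAP's COVID-19 protocol deviation terms already include discontinuation due to COVID-19.

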## **6.2 Secondary objectives**

Not Applicable.

Commercially Confidential Information

## **7 Statistical methods for safety and tolerability data**

All subjects within the safety analysis set will be included in the safety data analysis.

### **7.1 Variables**

The safety and tolerability variables are the number and severity of Adverse events (AEs)/Serious adverse events (SAEs), physical examinations, 12-lead ECG intervals (PR interval, QRS duration, heart rate, RR interval, QT interval and QTcF), vital signs (body temperature, height, weight, blood pressure and pulse rate), standard clinical laboratory evaluations (hematology, biochemistry and urinalysis), study-specific safety laboratory

evaluations as well as subject demographics, baseline characteristics, and treatment information. Comercially Confidential Information

## 7.2 Descriptive analyses

## Subject demographics and other baseline characteristics

Demographics and baseline characteristics variables are defined in Section 2. All data for background and demographic variables will be listed by treatment group and subject. Summary statistics will be provided overall and by treatment group. Categorical data will be presented as frequencies and percentages. For continuous data, mean, standard deviation, median, minimum and maximum will be presented.

Relevant medical histories, current medical conditions at baseline, results of laboratory screens and any other relevant information will be listed by treatment group and subject.

## Protocol deviations

In addition to the pre-defined standard protocol deviation terms, Novartis has defined 6 new protocol deviations and the corresponding relationship (health status related vs. site lockdown, subject concerns, etc.) to the COVID-19 pandemic in line with “Guidance on Conduct of Clinical Trials of Medical Products during the COVID-19 Public Health Emergency” (January 2021) from FDA and “Guidance on the Management of Clinical Trials during the COVID-19 (Coronavirus) Pandemic” (February 2021) from EMA as listed below.

- Missing visits
- Changes in procedures and assessments
- Planned visits not done at sites
- Changes in drug supply method
- Treatment not given
- Subject discontinuation due to COVID-19 situation

A summary table for the pandemic related/not pandemic related protocol deviations by category and relationship (and in total) will be provided by treatment group for all subjects randomized. For those related to the pandemic, “all COVID-19 pandemic related” protocol deviations will be summarized together and by specific type of reason (site issue, subject’s infection, etc.). The percentages will be calculated out of total randomized patients, to show how the pandemic related deviations impacted the study as a whole.

All protocol deviations will be listed. A separate listing will be provided for COVID-19 related protocol deviations.

## Treatment

Data for study drug administration and changes in dosage will be listed by treatment group and subject, including but not limited to:

- Dates of first and last exposure
- Any changes in dosage or missed doses (Y/N)?
- If changes in dosage or missed doses = Yes:

- Doses prescribed and administered (in mg)
- Total daily dose (in mg)
- Frequency of dosing
- Start and end dates of dose change
- Type of dose change
- Reason for dose change

Compliance to the study treatment data (% of missing doses and % of capsules taken with respect to the total number of expected doses/capsules during the treatment period) will not be analyzed or reported, the study drug accountability data not being captured in the CRF.

Concomitant medications prior to and after the start of the study treatment will be listed by treatment group and subject and summarized by treatment group for the safety analysis set.

### **Vital signs**

A listing will be provided presenting all vital signs measurements in a subject with any abnormal values (based on reference ranges). This listing will be sorted by treatment group, subject and visit/time. If there is any abnormality of a vital sign for a subject, all measurements of this vital sign for the subject will be presented in this listing. Abnormalities will be flagged using the following reference ranges:

Vital Sign Parameter	Reference Range
Systolic Blood Pressure	90-140 mmHg
Diastolic Blood Pressure	50-90 mmHg
Pulse Rate	40-90 bpm
Body Temperature	35.0-37.5 C

Baseline will be defined as the last available pre-dose measurement.

Summary statistics (absolute values) will be provided by treatment group and visit/time. Measurements obtained at Screening and EoS will be included in the tabulations for the overall safety population only.

### **Clinical laboratory evaluations**

A listing with laboratory parameters and their corresponding lab test codes (if applicable) and units will be provided for each lab category (hematology, biochemistry, and urinalysis).

A listing will be provided presenting all laboratory parameters in a subject with any out of range values. This listing will be sorted by treatment group, subject and visit/time for each lab category. If there is any abnormality of a parameter for a subject, all measurements of this parameter for the subject will be presented in this listing. Out of range values will be flagged as recorded in the database, e.g. for numerical results as "L" (for values lower than the lower limit of the reference range) and "H" (for values higher than the upper limit of the reference range).

Baseline will be defined as the last available pre-dose measurement.

Summary statistics (absolute values) of hematology and biochemistry tests will be provided by treatment group and visit/time. Measurements obtained at Screening and EoS will be included in the tabulations for the overall safety population only.

In particular, the following by-treatment summaries will be generated:

- Shift tables using the low/normal/high classification based on laboratory normal ranges to compare baseline to the worst on-treatment value (separately for hematology, biochemistry and urinary laboratory tests)

Commercially Confidential Information

Commercially Confidential Information

